### 13.1.5 Other Analyses

Using FAS, the followings shall be analyzed.

- 1) Efficacy endpoint: HbA1c

The mean and SD of HbA1c levels at each assessment time and changes in HbA1C from the baseline (Week 0) to each assessment time point will be calculated and represented in graphs.

- 2) Treatment compliance

Treatment compliance of each study subject will be calculated and summary statistics of compliance per treatment group will be presented.

## 13.2 Interim Analysis and Criteria for Early Termination

No interim analysis is planned.

## 13.3 Determination of Sample Size

60 subjects

<Rationale for the number of planned subjects>

By referring to the results of the questionnaire for treatment selection rate after dosing of once-weekly DPP-4 inhibitor, the treatment selection rate of once-weekly DPP-4 inhibitor is assumed to be 60%, treatment selection rate of daily DPP-4 inhibitor 20%, and rate of subjects who

do not show any preference for treatment (either is fine/prefer neither) 20%, respectively.

In doing so, a total of 54 subjects will be necessary in order to secure 90% power in the binomial test with two-sided significance level at 5%. With the estimated rate of discontinuation at 10%, the number of randomized subjects was set to be 30 subjects per group or 60 subjects in total.

## **14.0 QUALITY CONTROL AND QUALITY ASSURANCE**

### **14.1 Study-Site Monitoring Visits**

The sponsor or its designee shall perform periodic monitoring of study sites during the study to confirm that the study is conducted in accordance with all specifications in the protocol. In the monitoring, the data recorded on the CRF will be checked by comparing them with those in the source documents. Source documents are the original documents, data and records. The principal investigator and the chief executive of the study site shall ensure that the sponsor or its designee and the Ethics Review Committee, etc., have access to the source documents.

The sponsor or its designee shall access the records, including the list of subject ID codes, medical records of the subjects, and signed and dated original consent forms, to confirm that the study is appropriately conducted in compliance with the protocol. Also, confirm the consistency between CRF and the related source documents. The investigator, and other personnel involved in the study shall spare sufficient time to facilitate monitoring procedures during visits to the study site.

Detailed procedures for monitoring shall be described in a procedure manual prepared separately.

### **14.2 Deviation from the Ethical Guideline for Clinical Research and the Protocol**

The investigator shall record all deviations from the Ethical Guideline for Clinical Research and the protocol.

If any deviation is found, the principal investigator shall promptly notify the chief executive of the study site and the sponsor. As necessary, the principal investigator will discuss protocol revisions with the sponsor to reach agreement. For protocol revisions, draft revisions should be submitted as early as possible to the study site for approval of the committee such as ethics review committee.

### **14.3 Quality Assurance Audits and Regulatory Agency Inspections**

The sponsor or the designee shall perform audit at the study site as necessary. In such a case, the auditor designated by the sponsor shall contact the study site in advance to determine the date of audit. The auditor may ask to visit the facilities where laboratory specimens are collected and any other facilities used during the study. In addition, this study may be inspected by regulatory agencies, including those of foreign governments (e.g., the Food and Drug Administration [FDA], the United Kingdom Medicines and Healthcare products Regulatory Agency [MHRA]). If the study site is contacted for an inspection by a regulatory body, the sponsor should be notified promptly. The principal investigator and the chief executive of the study site shall ensure that the auditor has access to all the study-related source documents.

## **15.0 ETHICAL ASPECT OF THE STUDY**

This study shall be conducted with the highest respect for the individual participants (i.e., subjects) according to the protocol, the ethical principles that have their origin in the Declaration of Helsinki, and the Ethical Guideline for Clinical Research. Each investigator will conduct the study according to regulatory requirements and in accordance with “Responsibilities of the Investigator” that are listed in Appendix B.

### **15.1 IEC Approval**

The IEC, etc., shall be constituted in accordance with the regulations.

The sponsor or its designee should obtain the document listing the name and title of each committee member. When a committee member directly participates in this study, the document describing that he/she is not participating in deliberation or voting for the study will be obtained.

The sponsor or the designee shall provide related documents for review and approval of the protocol to the Ethical Review Board, etc. In addition to the protocol, a copy of the informed consent form and information sheet, written materials related to subject recruitment, advertisement, and other documents required by regulations, when necessary, shall be submitted to the central committee or a study site committee such as the Ethics Review Committee to obtain approval. The sponsor or the designee shall obtain records of approval by the Ethical Review Board, etc., for the protocol and the informed consent form and information sheet before the start of the protocol therapy. The records of approval by the Ethical Review Board, etc., shall include the study title, protocol number, preparation / revision date of the protocol, and version number and approval date of other reviewed documents (Example: informed consent and information sheet). The sponsor shall notify the study site and the investigator after confirming the validity of the regulatory documents of the study site. Protocol procedures such as obtainment of consent shall not be started until the study site and investigator receive notification.

The study site shall observe all requirements that the Ethical Review Board prescribes. The requirements may include notifications to committees such as ethics review committee, for example, revision of the protocol, revision of the informed consent form and information sheet, revision of materials related to subject recruitment, reports on safety in accordance with the regulatory requirements, reports on status of implementation of the study at intervals determined by a study site committee such as the Ethics Review Committee, and submission of the study completion report. The sponsor or its designee shall obtain written approval from a study site committee such as the Ethics Review Committee related to the above mentioned items and all related materials.

### **15.2 Conflict of Interests**

This study shall be conducted with the support of the sponsor.

Prior to the initiation of this study, the investigators involved in this study shall ensure appropriate management of any conflicts of interest (COI) in the conduct of the study in accordance with the rules of the study site.

The study site shall comply with all requirements specified by a committee such as an ethics review committee, including the COI self-statement form, the protocol, and the informed consent form and information sheet.

### **15.3 Informed Consent and Information Sheet, and the Agreement of the Subjects**

The informed consent and information sheet form shall contain specific requirements of the Declaration of Helsinki, Ethical Guideline for Clinical Research and all applicable laws and regulations. The informed consent form and information sheet shall specify the use of personal information and medical information of subjects in this study (both in and outside Japan: supply to a third party), and disclosure. The informed consent form and the information sheet will explain in detail the nature of the study, its objectives, and potential risks and benefits. The informed consent form will detail the requirements of the participant and the fact that subject is free to withdraw at any time without giving a reason and without any negative effect on the further medical care.

The principal investigator is responsible for the preparation, contents, and approval of the informed consent form and subject information sheet by the committee such as ethics review committee. The informed consent form and information sheet must be approved by the committee prior to use.

The informed consent form and information sheet shall be written in language that can be easily understood by the potential subjects. The investigator shall be responsible for providing detailed explanation of the informed consent form and information sheet to the potential subjects.

Information should be given in both oral and written form whenever possible and in manner deemed appropriate by the committee such as ethics review committee.

The investigator shall ensure that the potential subjects have (1) an opportunity to inquire about the study and (2) sufficient time to decide on their participation. If a potential subject decides to participate in the study, then the informed consent form must be signed and dated by the potential subject prior to entering into the study as a subject. The investigator shall instruct the potential subject to sign using their legal names, not nicknames, using a blue or black ball point ink pen. Also the investigator shall sign and date the informed consent form prior to entering into the study.

Once signed, the original informed consent form shall be retained by the investigator. The investigator shall record the date that the potential subject signed the informed consent form in the subject's medical record. A copy of the signed informed consent form shall be given to the subject. The investigator shall follow the same procedure as for obtaining the initial consent when newly obtaining re-consent from the concerned subject when the informed consent form is revised. The

date of obtaining new consent shall be recorded in the subject's medical record, and a copy of the revised consent form shall be provided to the subject.

#### **15.4 Personal Information of Subjects**

The sponsor or the designee shall affirm the principle of the protection of subjects' private/personal information. Throughout this study, subject ID codes shall be used to link the subject's source data to the sponsor's study database and study-related documents. Limited information on subjects such as gender, age, and date of birth may be used within the scope of all applicable laws and regulations for identification of subjects and confirmation of accuracy of subject ID code.

For verification of the conduct of the study in compliance with this protocol and the Ethical Guideline for Clinical Research, the sponsor shall require the principal investigator to provide the study sponsor's designee, representatives of regulatory authorities, designated auditors, and committees such as the Ethical Review Board direct access to subjects' original medical records (source data or documents), including laboratory test results, ECG results, admission and discharge records during a subject's study participation, and autopsy reports. The investigator shall obtain specific authorization of the subject as part of the informed consent process for access to subject's original medical records by study sponsor's designee and representatives of regulatory authorities (see Section 15.3).

When providing a copy of source documents to the sponsor, the investigator shall delete information that may lead to identification of an individual (name and address of subject, other personal information not recorded on the CRF of the subject).

#### **15.5 Consultation for Subjects or Persons Related to the Study**

The principal investigator shall establish a contact service to respond to inquiries concerning this study from subjects or concerned people. Details of the contacts for inquiries will be described in the informed consent form.

#### **15.6 Financial Burden or Reward to Subjects**

Regarding the expenses for this study, the sponsor shall pay for medical treatment not covered by health insurance and examinations necessary for the study as study expenses. The subjects shall pay expenses for medical treatment covered by ordinary health insurance.

In addition, the principal investigator shall pay expenses such as transportation expenses for participation in this study to the subjects at each visit from the study funds. Details of the financial burden on the subjects and rewards shall be described in the informed consent form and information sheet.

## **15.7 Benefits and Inconveniences to Subjects**

### **15.7.1 Benefits to Subjects**

The subjects will obtain detailed information on the status of their type 2 diabetes mellitus and their treatment satisfaction through participation in this study.

### **15.7.2 Inconveniences to Subjects**

Participation in this study may increase burden on the subjects due to requirement for answering questionnaires and DTSQ, as compared with routine medical practice.

## **15.8 Attribution of Study Results and Access Rights**

### **15.8.1 Attribution of Study Results**

The study results and data obtained from this study shall belong to the sponsor. In addition, secondary use (meta-analysis, etc.) of the data obtained in this study may be possible if used in such a way that the data shall not be linked to personal identification information.

### **15.8.2 Data Access Rights**

Access rights for all data and information generated from this study will be given to personnel approved by the sponsor.

## **15.9 Reporting of Results, Publication, Disclosure, and Clinical Study Registration Policy**

### **15.9.1 Reporting of Results, Publication and Disclosure**

The principal investigator shall report a written summary of results of the study to the chief executive of the study site and provide the sponsor with all the results and data obtained from the study. Only the sponsor may disclose the study information to other investigators or regulatory authorities during the study period, except when required by laws and regulations. The sponsor shall be responsible for publication of the protocol and study-related results (including the public web site) except for other cases permitted in the study contract.

During and after the study, the sponsor or its designee should promptly summarize the results and present them to medical journals and academic conferences, etc. The sponsor may publish any data or information obtained from the study (including data and information provided by the principal investigator) without obtaining agreement of the principal investigator.

The investigators should obtain the prior written approval from the sponsor when publishing the information obtained in this study at an academic conference, etc.

The sponsor shall report to the chief executive of the study site when final publication of the study results has been made.

### **15.9.2 Clinical Study Registration**

In order to ensure that information on clinical trials reaches the public in a timely manner and to comply with applicable laws, regulations and guidance, Takeda will, at a minimum register all interventional clinical trials it sponsors anywhere in the world on ClinicalTrials.gov and Japan Pharmaceutical Information Center Clinical Trials Information (JAPIC) before start of study. Takeda contact information, along with investigator's city, country, and recruiting status will be registered and available for public viewing.

### **15.9.3 Clinical Study Results Disclosure**

Takeda will post the results of clinical trials on ClinicalTrials.gov and JAPIC, as required by applicable laws and/or regulations.

### **15.10 Insurance and Compensation for Injury**

Each subject in the study must be insured in accordance with the regulations applicable to the site where the subject is participating. If a local underwriter is required, then the sponsor or sponsor's designee will obtain clinical study insurance against the risk of injury to study subjects. Refer to the study site agreement regarding the sponsor's policy on subject compensation and treatment for injury. If the investigator has questions regarding this policy, he or she should contact the sponsor or sponsor's designee.

**Appendix A Clinical Research Schedule**

Timing of visit	Week	Treatment			At discontinuation (c)
		0	8	16	
		Day	56	112	
Acceptable range (days)	-1	49-63	105-119	Until 14 days after the last dose	
Visit No.	1	2	3		
Informed consent	X				
Demographics and medication history	X				
Inclusion/exclusion criteria	X				
Questionnaire for patient background	X				
Physical examination	X	X	X	X	
Height / weight / BMI	X				
Concomitant medications (a)	X	X	X	X	
Concurrent medical condition	X				
HbA1c	X	X	X	X	
Prescription of study drug	X	X			
Treatment compliance		X	X	X	
DTSQ	X	X	X	X	
Questionnaire for patient preference			X		
Adverse event	X→	←X→	←X	←X	

(a) Record all concomitant medications.

(b) Start the dosing of the study drug from the following date after all tests at Week 0 are completed.

Set the start date of dosing as Day 1 and the day before the start date of dosing as Day 0.

(c) Conduct as much as possible.

2. ANALYSIS SET

- Full Analysis Set
The subjects who were randomized and given at least one dose of the study drug
- Safety Analysis Set
The subjects who were given at least one dose of the study drug

3. CONSIDERATIONS on STATISTICAL ANALYSIS

3.1. Adjustments for Covariates

Adjustment for covariates is not performed.

3.2. Handling of Dropouts or Missing Data

Missing values will not be complemented.

3.3. Criteria for Interim Analysis and Early Stopping

Interim analysis will be not performed.

3.4. Multicenter Study

Analyses for consideration of medical institution will not be performed.

3.5. Multiple Comparisons/Multiplicity

It does not adjust multiplicity.

3.6. Examination of Subgroups

Subgroup analysis will not be performed.

3.7. Considerations for Creating Analysis Results

- Confidence Coefficient
95% (two-sided estimation)
- Significance Level
The level of significance should be 5%.
- Summary Statistics
Number of Subjects, mean, SDs, Maximum values, Minimum values, and Quartiles
- Display Digit
 - [Mean, Confidence Coefficient, Quartiles]
Round statistics off to the 1 digits lower than significant digits of the data.
 - [Standard Deviation]
Round statistics off to the 2 digits lower than significant digits of the data.
 - [Minimum and Maximum Values]
Display the data at the significant digits.
 - [Proportion, Percentage]
Round off 2 decimal places and display up to 1 decimal place.
 - [p-value]
Round off 5 decimal places and display up to 4 decimal places. However, when the p-value is less than 0.0001, it is expressed as "p <0.0001".

3.8. Time Window

For each inspection, observation and evaluation item, evaluable data is handled according to the following table. Administration of the study medicine starts from the day after completion of all the examination of Week 0. The date of the first dose is defined as "Day 1" and the day before of the first dose is defined as "Day -1". The criteria of adoption of data on the data obtained after discontinuation in discontinued subjects are as follows.

- HbA1c (NGSP) :
If data up to 14 days after the last dose is included in a time window, it is treated as data of that visit.
- DTSQ treatment satisfaction and Medication Compliance:
As long as the criteria for the analysis set is satisfied, if an evaluation date is included in a time window, it is treated as data of that visit.

When there are multiple data that can be evaluated at the same visit, the one with the closest inspection date, observation date and evaluation date to the reference implementation date is adopted. If the magnitude of the difference from the reference implementation date is the same, the later data is adopted.

The 16th week (Week 16) of the treatment period in the following analysis is handled as the visit of 8 weeks after start of administration of the study drug after switching.

[HbA1c (NGSP), DTSQ treatment satisfaction]

Visit	Reference Date	Time Allowance
Week 0 of the Treatment Period	Number of days after administration: -1	-1
Week 8 of the Treatment Period	Number of days after administration: 56	49 - 63
Week 16 of the Treatment Period	Number of days after administration: 112	105 - 119

[Medication Compliance]

Visit	Reference Date	Time Allowance
Week 8 of the Treatment Period	Number of days after administration: 56	49 - 63
Week 16 of the Treatment Period	Number of days after administration: 112	105 - 119

4. SUBJECTS, DEMOGRAPHIC and OTHER BASELINE CHARACTERISTICS

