### 9.1.8 DTSQ

Subjects will answer the DTSQ (all 8 questions) regarding the diabetes therapy being conducted at each assessment time point during the treatment period. The investigator will instruct the subjects to answer all questions truthfully and record the answer of each question of the DTSQ (8 questions in total) on the CRF.

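### SAP 3.8 chooses the Week 8 record by closeness to Day 56 without reference to the switch, so a record made on the second drug can be reported under the first

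*SAP*

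**What the plan says.** SAP 3.8 sets study-day windows counted from the first dose of the first drug. Week 8 has the reference "Number of days after administration: 56" and an allowance of Days 49-63. Week 16 has reference Day 112, allowance Days 105-119, and "is handled as the visit of 8 weeks after start of administration of the study drug after switching". By implication, Week 8 is the first drug's 8-week result. SAP 5.3.1 to 5.3.3 tabulate DTSQ satisfaction, HbA1c and compliance by study drug on that basis.

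For data obtained after discontinuation there are two rules:

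- HbA1c: "If data up to 14 days after the last dose is included in a time window", it is used for that visit.
- DTSQ and compliance: "As long as the criteria for the analysis set is satisfied, if an evaluation date is included in a time window", the record is used for that visit.

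The analysis set for all three measures is the Full Analysis Set (SAP 2), defined as "The subjects who were randomized and given at least one dose of the study drug".

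Where several records fall in one window, "the one with the closest inspection date, observation date and evaluation date to the reference implementation date is adopted". For two records equally far from the reference day, SAP 3.8 adds a tie rule: "If the magnitude of the difference from the reference implementation date is the same, the later data is adopted".

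Protocol 9.3.2, 9.3.4 and Appendix A collect all three measures at Visit 2 and again at discontinuation. Appendix A allows Visit 2 on Days 49-63 and the discontinuation visit up to 14 days after the last dose, with a footnote asking only that it be done as far as possible. Protocol 9.1.8 has subjects answer the DTSQ "regarding the diabetes therapy being conducted at each assessment time point during the treatment period".

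**The concern.** The switch happens at Visit 2, and Visit 2 may take place anywhere in the Week 8 window. The second drug can therefore be started while that window is still open. SAP 3.8 compares candidate records only by distance from Day 56; it does not look at the switch date or at the drug being taken. A discontinuation record made shortly after the switch can then replace the Visit 2 record, although Visit 2 is the assessment designed to close the first period. The first drug's summary would contain a response given on the other drug, and the correct response, which was collected, would be dropped.

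The DTSQ is the most exposed measure because it asks about current therapy. Compliance is confirmed at every visit (Protocol 9.2). A record made after Visit 2 would ordinarily describe the drug taken since then, although no reference period is stated.

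The secondary issue concerns subjects who stop and do not switch. HbA1c has an explicit limit on time since the last dose. The DTSQ has none in the SAP, although an answer given after stopping no longer describes the study drug.

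**Working it through.** The plan gives no figure for this point, so the stated rule is applied directly.

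**Inputs**

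- Week 8 window Days 49-63, reference Day 56 (SAP 3.8). Visit 2 has the same range (Protocol Appendix A).
- Nearest record wins and ties go to the later (SAP 3.8).
- Full Analysis Set membership needs one dose (SAP 2), so it excludes no post-switch record.
- 60 randomized, 10% estimated discontinuation (Protocol 13.3).
- Assumption: the second drug has been started by the day of the later record.

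**Step 1. Selection rule.** Let v be the day of Visit 2 and d the day of a later record in the window. The later record is adopted when |d − 56| ≤ |v − 56|.

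- v = 54, d = 57: 1 ≤ 2, so Day 57 replaces Visit 2.
- v = 54, d = 58: 2 = 2, a tie, so Day 58 replaces Visit 2.
- v = 54, d = 59: 3 > 2, so Visit 2 is kept.

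**Step 2. All day pairs.** For v before Day 56, put k = 56 − v. Later days available: 63 − v = 7 + k. Days on which the later record wins: v + 1 to 56 + k, which is 2k days.

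| Visit 2 day | Later days available | Later record adopted |
|---|---|---|
| 49 | 14 | 14 |
| 50 | 13 | 12 |
| 51 | 12 | 10 |
| 52 | 11 | 8 |
| 53 | 10 | 6 |
| 54 | 9 | 4 |
| 55 | 8 | 2 |
| 56-62 | 7+6+5+4+3+2+1 = 28 | 0 |
| Total | 77 + 28 = 105 | 56 |

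From Day 56 onward a later record is always further from the reference, so Visit 2 is kept. If the Visit 2 record is missing, any later record in the window is used, whatever the day of Visit 2.

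**Step 3. HbA1c.** Its limit runs from the last dose and names no drug. With Visit 2 on Day 54, a last dose of the second drug on Day 56 and a sample on Day 57, the gap is 57 − 56 = 1 day, well inside 14. The limit does not prevent the substitution.

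**Step 4. Number of subjects.** Expected discontinuations are 0.10 × 60 = 6. Displacement also needs an early Visit 2 and a further assessment no more than 63 − 49 = 14 days after it. The documents give no timing of discontinuation, so no expected count can be derived.

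**Step 5. Effect of a switch-date condition.** If a Week 8 record must be dated on or before the first dose of the second drug, the later record is ineligible in every pair: 56 falls to 0 of 105.

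**Step 6. DTSQ after stopping.** Under the SAP wording alone, the longest gap in the Week 8 window is 63 − 1 = 62 days (last dose Day 1, answer Day 63). With the HbA1c limit it is 14 days. A last dose on Day 36 and a visit on Day 50 give exactly 14 days, which both the limit and Appendix A accept.

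**The case against.** The strongest reply is that the case is remote. A subject must attend Visit 2 early, start the second drug, stop within days and be assessed again by Day 63. Visits are aimed at Day 56, where the problem disappears. This stands, and it limits the point to a minor one. It does not remove it, because when the case arises the stated rule gives the wrong answer.

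Several stronger readings are tempting but unsupported:

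- **56 of 105, or 53%, as a risk.** The count weights all day pairs equally and says nothing about how often they occur.
- **Six subjects as a ceiling.** Protocol 13.3 estimates a rate and sets no maximum. Equally, most discontinuers need not have an assessment in the relevant days.
- **Answers after stopping counted without limit.** The SAP states no limit for the DTSQ, but Appendix A restricts the discontinuation visit to 14 days after the last dose. If that is followed, adding the limit to the SAP excludes nothing. It matters only for a late visit that still falls in a window.
- **The same objection for compliance after stopping.** Compliance classifies study drug already taken (Protocol 9.2). The current-therapy argument does not reach it.
- **Discontinuers as the most dissatisfied subjects.** The documents do not say so. The reasons in Protocol 7.5 include pregnancy, loss to follow-up and study termination.

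**Conclusion.** The point holds as a minor error in a stated rule. For DTSQ, compliance and HbA1c alike, SAP 3.8 can discard a valid Visit 2 record and report one made on the second drug as the first drug's 8-week result. Displacement requires Visit 2 on Days 49-55 and a later record, normally a discontinuation assessment, by Day 63 with the second drug already started.

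Very few subjects should be affected. The measures are additional endpoints, reported as summary statistics or proportions without a test. A reader might infer that the treatment comparison is at risk. It is not: the preference analysis in SAP 5.1.1 and the sample size do not use these records.

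The missing 14-day limit for the DTSQ is secondary. It is an inconsistency with the HbA1c rule, and Appendix A already bounds it when followed.

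**What to change.** Add to SAP 3.8:

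1. For DTSQ, compliance and HbA1c, a record is eligible for Week 8 only if dated on or before the first dose of the second drug. The nearest-date and tie rules apply among eligible records only.
2. A later record inside the Week 8 window is not used for Week 8. It counts for the second drug only if it falls in the Week 16 window. It should not be moved to the second drug automatically, because a value a few days after the switch is not that drug's 8-week result.
3. DTSQ records after discontinuation are used only up to 14 days after the last dose, as for HbA1c and consistent with Appendix A.

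The cost is a date check in the program. A few values may become missing, where Visit 2 was not recorded or a discontinuation visit was late; SAP 3.2 does not impute them.

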### 9.3.4 Discontinuation

Tests, observations and evaluations performed at the discontinuation are shown below.

- Physical examination
- HbA1c
- DTSQ
- Concomitant medication (a)
- Treatment compliance
- Questionnaire for patient preference for treatment

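### SAP 3.8 places DTSQ, compliance and HbA1c values by calendar window only, so discontinuation assessments outside Days 49-63 and 105-119 are listed but enter no per-drug summary, and one inside can be credited to the wrong drug

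*SAP*

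**What the plan says.** **Collection.** Protocol 9.3.4 introduces its list with "Tests, observations and evaluations performed at the discontinuation are shown below"; the list includes HbA1c, DTSQ and treatment compliance. Appendix A allows this assessment up to 14 days after the last dose, and a footnote asks for it only as far as it can be done.

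**Placement.** SAP 3.8 defines two post-baseline windows, Days 49-63 (reference Day 56) and Days 105-119 (reference Day 112). For data obtained after discontinuation, the DTSQ and compliance rule is that "if an evaluation date is included in a time window, it is treated as data of that visit". The HbA1c rule is "If data up to 14 days after the last dose is included in a time window, it is treated as data of that visit". If several values fall in one window, the one nearest the reference day is used, and a tie goes to the later one. Week 16 is treated as 8 weeks on the second drug. There is no early-termination visit and no rule for a value outside the windows.

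**Summary.** SAP 5.3.1 to 5.3.3 summarise each measure per drug, in the Full Analysis Set, only at 8 weeks on that drug. SAP 3.2 adds "Missing values will not be complemented". Protocol 13.1.5 says "Treatment compliance of each study subject will be calculated and summary statistics of compliance per treatment group will be presented".

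**Listing.** SAP 7 lists DTSQ, HbA1c and compliance for the Full Analysis Set. SAP 4.1.4 tabulates incomplete treatment with reasons.

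**The concern.** A value that sites are asked to obtain when a subject stops a drug reaches a summary only if its date happens to fall in one of two 15-day windows. A subject who stops on Day 30 or Day 85 and is assessed on that day contributes nothing to the table for the drug stopped. The table nevertheless carries the Full Analysis Set label, and the protocol speaks of compliance for every subject.

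DTSQ and compliance are the natural context for a preference result, and the protocol's Background expects weekly dosing to improve adherence and help prevent discontinuation. Early stoppers bear directly on that expectation. If their satisfaction or compliance differs from that of subjects who reach 8 weeks, the per-drug summary will not show it.

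A second problem has the same cause. Placement looks at the calendar day and not at the drug being taken, so a value obtained on the second drug can fall in the window that represents the first.

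**Working it through.** **Expected discontinuers.** Protocol 13.3 gives 54 evaluable subjects and 10% discontinuation. 54 / (1 - 0.10) = 60, which reproduces the planned total. Expected discontinuers: 0.10 x 60 = 6.

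**Share of discontinuation assessments inside a window.** The documents do not say when subjects stop. Assume the last-dose day T is even over Days 1-111 and the assessment falls L days later, with L from 0 to 14 as Appendix A allows. The assessment counts if T + L lies in 49-63 or 105-119.

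| Lag L | Days T in first window | Days T in second window | Share in a window | Left out | Of 6 |
|---|---|---|---|---|---|
| 0 | 15 (T = 49-63) | 7 (T = 105-111) | 22/111 = 20% | 80% | 4.8 |
| 7 | 15 (T = 42-56) | 14 (T = 98-111) | 29/111 = 26% | 74% | 4.4 |
| 14 | 15 (T = 35-49) | 15 (T = 91-105) | 30/111 = 27% | 73% | 4.4 |

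With L spread evenly over 0-14, 25% are in a window. Counting only last doses up to Day 104, the share in a window runs from 15/104 = 14% (L = 0) to 29/104 = 28% (L = 14), so 72-86% are left out. The in-window counts are generous: at L = 0 they include Days 57-63, which follow a Day 56 switch and so lie in the first drug's window.

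**Numbers in each drug's table.** Take the same assumptions, with stoppers balanced over the two sequences. A discontinuer has a Week 8 value if T is at least 56 or the assessment falls in 49-63. That is 63/111 of days at L = 0 and 71/111 at L = 14, or 3.4 to 3.8 of the 6. A Week 16 value exists for 7/111 to 15/111, or 0.4 to 0.8 of the 6. Each drug's table then holds

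- L = 0: 54 + (3.4 + 0.4)/2 = 55.9
- L = 14: 54 + (3.8 + 0.8)/2 = 56.3

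So about 56 subjects per drug are summarised, against 54 if only completers counted. About half the stoppers (56/111) have their last dose by Day 56 and never start the second drug. About 60 - 3/2 = 58.5 subjects therefore take each drug, and two to three per drug have no summarised value for it.

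**Misplacement.** Suppose Visit 2 is on Day 49, which is allowed. The subject switches, takes the last dose of the second drug on Day 58 and is assessed on Day 60. Both values lie in 49-63. Distances from Day 56 are |49 - 56| = 7 and |60 - 56| = 4, so SAP 3.8 takes the Day 60 value as Week 8. The first drug's table receives a value obtained after the second drug, and the Visit 2 value drops out. In general, a discontinuation value on Day D displaces a Visit 2 value on Day V (V below 56) when D is at most 63 and |D - 56| is no larger than 56 - V, because ties go to the later value.

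**The case against.** **These are 8-week analyses.** The three SAP 5.3 headings specify 8 weeks on each drug, and a Day 10 or Day 85 value is not an 8-week value. Summarising observed data at a stated visit without imputation is a coherent choice. This stands, and it is why the 8-week row should stay.

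**A reader might infer that the tables describe completers only.** The documents do not support that. A subject who finishes period 1 and stops in period 2 normally keeps the Week 8 value for the first drug, and SAP 3.8 expressly accepts in-window values from discontinued subjects.

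**A reader might infer that the values are discarded.** They are not: SAP 7 lists them. The listing may also be enough to meet the protocol's wording on compliance of each subject, so no clear contradiction with Protocol 13.1.5 is shown.

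**A reader might infer a bias towards one drug.** That cannot be shown. Nothing in the documents says early stoppers are less satisfied; Protocol 7.5 also lists adverse events, pregnancy, protocol deviation and study termination as reasons. If three omitted subjects scored 12 DTSQ points lower, the mean over 60 would move by 3 x 12 / 60 = 0.6 points, but both inputs are assumed. If the other three of the six stopped the other drug with similar scores, both means would shift alike.

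**Values may not exist, or may be in a window.** Collection at discontinuation is on a best-effort basis, and subjects lost to follow-up may have none. With only three visits, stopping recorded at the Week 8 visit would be in window. Both points stand and reduce the number affected.

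**Conclusion.** The gap is real and minor. No rule in the SAP brings an out-of-window discontinuation value into a 5.3 summary, so the per-drug tables describe subjects assessed about 8 weeks into that drug, under a Full Analysis Set label that suggests wider coverage. With even stop timing over Days 1-111, about 73-80% of discontinuation assessments are left out, roughly 4-5 of the 6 expected discontinuers; the number is smaller if assessments are missed or if stopping clusters at the Week 8 visit. The direction and size of any effect on the means cannot be derived from the documents.

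The misplacement follows from the written rule whatever the overall timing, but it needs an early Visit 2 and a quick stop of the second drug, so it should be rare.

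DTSQ and HbA1c are additional endpoints, compliance falls under other analyses, and SAP 5.3 plans no tests or confidence intervals for them. Preference is not in the SAP 3.8 window tables, so the primary analysis and the sample size are unaffected.

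**What to change.** **SAP 3.8.** State that an assessment at discontinuation, made within 14 days of the last dose, is assigned to the drug of the last dose whatever its calendar day, and never replaces a visit value belonging to the other drug.

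**SAP 5.3.1 and 5.3.3 (optionally 5.3.2).** Keep the 8-week row. Beside it add a supplementary row, Week 8 of the drug or at discontinuation, which uses the 8-week value where there is one and the discontinuation value otherwise. Give the number of early stoppers per drug, with and without a value, so that the reader can see how far each table falls short of the Full Analysis Set.

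**Cost.** The change needs a short addition to SAP 3.8, one extra row in two or three tables and one count. It needs no new data collection, because it uses whatever was obtained at discontinuation. The drawback is mixed length of exposure in the new row, which is why it supplements the 8-week row and does not replace it.
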